## 7.2 *Non-Compartmental Analysis (NCA)*

Hypothesis of the proposed research is that the three test formulations (differing in the c/p ratio) will differ in AUC and Cmax estimates. Three multiple comparisons will be performed i.e. Reference against the reference, reference against test 1 and reference against test 2. A multiplicity adjustment (e.g. bonferroni type) will be made for the 3 multiple comparisons. No additional adjustment will be made for the use of multiple metrics. NCA will be performed in WinNonlin using an inbuilt extra-vascular PK model. Standard PK metrics such as  $AUC_{(0-30min)}$ ,  $AUC_{(0-t)}$ ,  $AUC_{(0-inf)}$ ,  $C_{max}$ ,  $t_{max}$ , terminal slope/half-life,  $CL/F$ ,  $Vdss/F$ ,  $AUMC_{(0-t)}$ ,  $AUMC_{(0-inf)}$ , and MRT will be calculated for each individual plasma-concentration-time profile. ANOVA model will be used to construct univariate 90% confidence intervals for  $AUC_{(0-t)}$  and  $C_{max}$  ratios and applied to conventional 0.8 – 1.25 average BE limits. If needed, alternative BE evaluation methodology and or BE criteria may be investigated. Data will also be assessed by ANOVA methods (SAS 9.2 or another equally suitable software package) to test for statistical differences ( $p<0.05$ ).

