## 2. Glossary

### List of Abbreviations and Definitions of Terms

ANOVA	Analysis of Variance
APSD	Aerodynamic Particle Size Distribution
AUC (0-t)	Area under the concentration of analyte vs. time curve (AUC) from time zero to the last quantifiable concentration
AUC (0-inf)	AUC from time zero extrapolated to infinity
AUMC (0-t)	Area under the moment curve from time zero to the last observation
AUMC (0-inf)	Area under the moment curve when the concentration time curve is extrapolated to infinity
BE	Bioequivalence
BMI	Body Mass Index
β-hCG	Serum beta-human chorionic gonadotropin
C max	The peak or maximum concentration
CL/F	Ration of the total body clearance and the fraction of dose absorbed (F)
DPI	Dry Powder Inhaler
ECG	Electrocardiogram
ED	Emitted Dose
FEV1	Forced Expiratory Volume in 1 second
FDA	Food and Drug Administration
FP	Fluticasone Propionate
PPF I	100 mcg Fluticasone Propionate Formulation 1
PPF II	100 mcg Fluticasone Propionate Formulation 2
PPF III	100 mcg Fluticasone Propionate Formulation 3
PPF III*	100 mcg Fluticasone Propionate Formulation 3 replicate
GLP	Good Laboratory Practices
GSD	Geometric Standard Deviation
ISM	Impactor-Sized Mass
IUD	Intrauterine Device
Lamda Z	First order rate constant associated with the terminal (log-linear) elimination phase
LC-MS/MS	Liquid Chromatography – Mass Spectroscopy/Mass Spectroscopy
MMAD	Mass Median Aerodynamic Diameter
MRT	Mean Residence Time, is the amount of time a particle remains in a system , calculated as AUMC/AUC
NCA	Non Compartmental Analysis
t max	The time of peak concentration
VZ/F	Volume of distribution based on the terminal phase corrected with F

\* The asterisk is used to distinguish the replicate from the original formulation.

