### 3. Study Design

The study comprises of 5 visits: 1 screening visit and 4 study visits.

On each study visit day, subjects will get 5 inhalations from one of the following formulations:

Study Drug	Device	Formulation
1	Plastiape Monodose DPI	Fluticasone Propionate Formulation 1 (FPF I)
2	Plastiape Monodose DPI	Fluticasone Propionate Formulation 2 (FPF II)
3	Plastiape Monodose DPI	Fluticasone Propionate Formulation 3 (FPF III)

The following sequences will be used in the study:

Sequence	Study Visit 1	Study Visit 2	Study Visit 3	Study Visit 4
1	FPF I	FPF II	FPF III	FPF III*
2	FPF II	FPF III*	FPF I	FPF III
3	FPF III	FPF I	FPF III*	FPF II
4	FPF III*	FPF III	FPF II	FPF I

Note that in this design every study drug appears once in each period. Also every study drug is immediately followed only once by each of the other study drugs.

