## **5.2 *Study Visits 1, 2, 3 and 4***

Eligible subjects will be asked to return for study visit 1 (see Appendix A for location). A minimum period of 5 days should lapse between the subsequent study visits. Each study visit is scheduled for 28 hours over two days. The study will be conducted at the UF CRC (Clinical Research Center). It is an outpatient study and the subject will be asked to come back the following day for the 24 hour blood sample. The subject will be asked to stay in an outpatient room during the study visit. The same activities are carried out at the other study visits.

At each study visit, changes in medical history including concomitant medications will be documented. Vital signs will be obtained. Inhalation training will be provided to the subjects as mentioned in the section above. An IV catheter will be inserted in a vein located in the forearm region of the subject. The IV catheter is used to avoid multiple pricks while collecting blood samples. The IV catheter is not used for the administration of the drug. The subject inhales 5 times from a given inhaler during each study visit. Each inhaler will be used only once and by only one subject to ensure the subject's safety from infectious agents. The schedule below summarizes the procedures performed at the screening visit and a single study visit.

Activity	Screening Visit	Study Visit	
Visit Window (Days)	2-28 Days prior study visit	Day 1	Day 2
Subject Information	X		
Informed Consent	X		
Review Inclusion/Exclusion Criteria	X		
Demographic Data	X		
Medical History	X	X	
Concomitant Medications	X	X	X
Measure BMI	X		
Vital Signs	X	X	
Physical Examination	X		
Lung Function Measurements (FEV1)	X		
Pregnancy Test	X	X	
Laboratory Assessments	X		
ECG	X		
Adverse Events	X	X	X
Proper Inhalation Technique	X	X	
Inhalation of Study Formulation		X	
Blood Sampling for PK		X	X

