## 7.3 *Compartmental Analysis*

In addition to NCA analysis, compartmental data analysis methodology will be applied to the observed in vivo pharmacokinetic (PK) data. Compartmental PK analysis using NONMEM (or another equally suitable software package) will incorporate information on physiological processes such as pulmonary absorption, mucociliary clearance rates and dissolution rates (bulk and after cascade impactor separation), and cascade impactor information.

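### The protocol plans a steady-state volume (Vdss/F) from inhaled data alone; computed with the protocol's own MRT it would include absorption time and overstate the volume, though only as a descriptive parameter

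*Protocol*

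**What the plan says.** Protocol section 7.2 and the Statistical Methods part of the synopsis give the same list of non-compartmental parameters for each individual profile. It includes CL/F, Vdss/F, AUMC to the last sample and to infinity, and MRT. The method is stated in 7.2: "NCA will be performed in WinNonlin using an inbuilt extra-vascular PK model".

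Four other statements bear on the volume term:

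- Route, protocol section 3: "On each study visit day, subjects will get 5 inhalations from one of the following formulations". Section 5.2 adds: "The IV catheter is not used for the administration of the drug". No period has intravenous dosing.
- MRT, glossary: "Mean Residence Time, is the amount of time a particle remains in a system , calculated as AUMC/AUC". Absorption time is not subtracted.
- Volume, glossary: the only volume defined is VZ/F, described as "Volume of distribution based on the terminal phase corrected with F". Vdss/F is not defined anywhere.
- Absorption, section 7.3: the compartmental analysis "will incorporate information on physiological processes such as pulmonary absorption, mucociliary clearance rates and dissolution rates". That analysis is separate from the non-compartmental one.

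SAP section 4.1 limits the ANOVA to Cmax, AUC0-last and AUC0-inf. It promises descriptive statistics for all PK parameters and sends the non-compartmental results to the FDA before unblinding. The SAP does not name Vdss/F, MRT or AUMC.

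**The concern.** Steady-state volume is clearance multiplied by the mean residence time of disposition, that is, the time a molecule spends in the body once it has been absorbed. After inhalation AUMC/AUC also counts the time taken to dissolve and cross the lung. Removing that part needs intravenous data or a disposition model, and the non-compartmental plan has neither.

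The trial's hypothesis is that "the three test formulations (differing in the c/p ratio) will differ in AUC and Cmax estimates". Formulations that deposit differently may well be absorbed at different rates. Part of such a difference would then be reported under the name of a distribution volume. The value would also sit in the parameter set sent out before unblinding, with nothing to warn the reader that absorption time is in it.

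**Working it through.** The documents state no value for Vdss/F, MRT, MAT or half-life, so there is no figure of the plan's to reproduce.

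**Identity.** Here Vdss/F is taken to mean steady-state volume over F, computed with the protocol's MRT.

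- True value: Vss/F = CL/F x MRT(disposition).
- After inhalation: AUMC/AUC = MRT(disposition) + MAT.
- Hence CL/F x AUMC/AUC = Vss/F x (1 + MAT/MRT(disposition)).

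The factor exceeds 1 for any positive MAT. It does not contain F.

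**Size over assumed ranges** (MAT 0.5–8 h, disposition MRT 4–12 h). Entries are 1 + MAT/MRT:

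| Disposition MRT | MAT 0.5 h | MAT 2 h | MAT 8 h |
|---|---|---|---|
| 4 h | 1.125 | 1.50 | 3.00 |
| 8 h | 1.06 | 1.25 | 2.00 |
| 12 h | 1.04 | 1.17 | 1.67 |

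The extremes are 1 + 0.5/12 = 1.04 and 1 + 8/4 = 3.00, an overstatement of about 4% to 200%.

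**Numerical check on the protocol's sampling times.** A two-compartment model with first-order absorption was sampled at the pre-dose time and the 17 post-dose times. It used the linear trapezoidal rule and a terminal slope from the last four samples. All parameters are arbitrary assumptions: CL 60 L/h, central volume 100 L, peripheral volume 300 L, inter-compartmental clearance 60 L/h, F = 0.10. Disposition MRT is then 400/60 = 6.67 h, and true Vss/F is 400/0.10 = 4000 L. True VZ/F is 6541 L.

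| MAT | CL/F x AUMC/AUC | Ratio to true Vss/F | VZ/F |
|---|---|---|---|
| 0.5 h | 4153 L | 1.04 | 6439 L |
| about 1 h | 4439 L | 1.11 | 6432 L |
| 2 h | 4993 L | 1.25 | 6215 L |
| 4 h | 6130 L | 1.53 | 6091 L |
| 6.67 h | 8020 L | 2.00 | 7430 L |

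The ratios at 1 to 4 h lie a little under the identity (at 4 h, 1 + 4/6.67 = 1.60) because of the sampling grid and the fitted slope.

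Two things follow. With disposition and F held fixed, moving MAT from 1 to 4 h raises the supposed steady-state volume by 6130/4439 – 1 = 38%, while VZ/F moves by 6091/6432 – 1 = –5%. VZ/F is not immune, however: at MAT 6.67 h it is 7430/6541 – 1 = 14% too high, because slow absorption has entered the terminal slope.

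**Separating F.** With F = 0.15 the true Vss/F is 2667 L, and the values at 1 and 4 h become 2959 and 4087 L. The ratios to truth stay at 1.11 and 1.53. A difference in F rescales the volume; the absorption term is a further, separate distortion.

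**The case against.** The strongest reply is that nothing the trial decides depends on this parameter, and that stands. The hypothesis concerns AUC and Cmax, the 90% intervals in 7.2 are for AUC(0-t) and Cmax, and the SAP's ANOVA covers Cmax and two AUCs. The sample size in 7.1 cites Cmax and tmax. Section 7.2 also mentions ANOVA for statistical differences without naming the metrics, but the SAP settles which ones are tested.

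A second reply is that no formula for Vdss/F is given. Since the glossary defines only VZ/F, the listing may be a naming slip. That is plausible. If so, the computed value may be sound and only the label wrong, and the same edit cures it.

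A third is that VZ/F has weaknesses of its own. It does: it also varies with F, and the check above shows that slow absorption can affect it. It simply lacks the added MRT term.

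Several stronger readings are tempting but not supported:

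- *Any formulation difference in the reported volume would be impossible.* The parameter is volume divided by F. Fine particle dose below 5 µm in SAP Table 1 ranges from 12.230 to 18.707 µg, a ratio of 1.53, so F may well differ between formulations and the parameter with it.
- *The volume will be inflated two- or three-fold.* That needs a MAT as large as, or twice, the disposition MRT. The documents give neither quantity.
- *Most of AUMC lies beyond the last sample at 24 h.* For a single exponential with rate constant k, the share is exp(–24k)(1 + 24k): 8%, 24%, 38.5% and 66.7% at half-lives of 4, 6, 8 and 14 h. The documents state no half-life.
- *The difference in AUMC/AUC should become an absorption endpoint, limited to well-extrapolated profiles.* This is a preference. Absorption is already addressed in the compartmental analysis, and such a filter has no stated threshold and could selectively remove slowly absorbed profiles.
- *The extravascular model is the mistake.* It is appropriate for inhaled drug; the fault is the volume listed after it.

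**Conclusion.** The point holds as a minor error in a descriptive parameter. The protocol commits to Vdss/F for every profile, all dosing is inhaled, and the only MRT it defines includes absorption time. If the volume is built from that MRT, it overstates Vss/F by the factor 1 + MAT/disposition MRT. The direction follows from the identity. The size, about 4% to 200%, rests entirely on the assumed ranges.

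That the bias differs between formulations rests on a further assumption, that their absorption times differ. The deposition hypothesis makes this plausible, but the documents do not quantify it. Bioequivalence conclusions, confidence intervals and sample size are unaffected.

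**What to change.** In the synopsis (Statistical Methods) and in section 7.2, replace Vdss/F with VZ/F as the glossary already defines it. Label it apparent, with a note that it depends on F and on a terminal slope that slow lung absorption may set. In the glossary and wherever MRT is reported, describe AUMC/AUC as mean residence time after inhalation, including absorption time.

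The cost is a few words in the protocol and one output setting; no samples or new analyses are needed. The SAP needs no correction on this point, because it names none of these parameters. The downside is that no steady-state volume is reported.

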## 7.3 *Compartmental Analysis*

In addition to NCA analysis, compartmental data analysis methodology will be applied to the observed in vivo pharmacokinetic (PK) data. Compartmental PK analysis using NONMEM (or another equally suitable software package) will incorporate information on physiological processes such as pulmonary absorption, mucociliary clearance rates and dissolution rates (bulk and after cascade impactor separation), and cascade impactor information.

Data analysis plan

Pharmacokinetic Comparison of Locally Acting Orally Inhaled Drug Products ('DPI study', FDA BAA-16-00122)

1. Purpose

This document describes the non-compartmental data analysis plan for the above mentioned clinical trial. This clinical pharmacokinetic (PK) study assessed three fluticasone propionate DPI formulations (formulation 1, 2, 3) which have been characterized through *in vitro* methods. These formulations were compared in the present double-blind, randomized 4-way cross-over study; one formulation was repeated to evaluate intra-subject variability; this replicated formulation is named 3a and 3b.

2. Objectives

The primary aim of this research study is to aid the FDA in finding methods to ensure that the versions of generic drugs that are inhaled (for example, drugs used to treat asthma) are bioequivalent to the trade name drug. As a part of the research study, pharmacokinetic (PK) studies (studies measuring drug levels in the blood over time after inhalation) will be done using three different versions of fluticasone propionate (FP, a drug routinely used in asthmatic patients) administered using a dry powder inhaler (DPI, an inhalation device that delivers the drug as a dry powder).

3. Available *in vitro* data and proposed normalization

We will use the formulation with the largest Median Mass Aerodynamic Diameter (MMAD) as reference (**Table 1**).

Table 1: Summary of FPD data averaged over the 12 and 20 month time points

Formulation	FPD (<5 µm) (µg)	FPD (<3 µm) (µg)	MMAD (µm)
15-mm-016	18.707	9.977	3.77
15-mm-017	12.230	5.274	4.53
15-mm-015	15.869	8.599	3.73

We expect that the c/p ratio is determined by the MMAD with larger particles being deposited more centrally compared to smaller particles.

We will use three approaches of normalizing the PK parameters:

- 1) Normalization based on the ex-throat data
- 2) Normalization based on fine particle dose (FPD <3 µm) data
- 3) Normalization based on fine particle dose (FPD <5 µm) data

Normalization factors for the ex-throat data will be calculated separately for the VCU, AIT and OPC throats. The average normalization factors over the three throats will be used for the normalization using this approach. The normalization factors from this ex-throat approach will be used for the **primary analysis**.

For the FPD <3 μm and FPD <5 μm normalization, we will average the respective FPD data at the 12 and 20 month stability time-points. These two time-points include the time of the clinical trials performance. The 15-mm-017 formulation will be used as reference (i.e. normalization factor is defined as 1.0). Normalization factors using the FPD approach will be used as secondary analyses.

4. Methods

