4.1. Non-compartmental pharmacokinetic analysis

Non-compartmental analysis (NCA) will be performed as described previously.¹ The NCA PK parameters will be calculated for each subject and study period using the formulas implemented in the Phoenix / WinNonlin Professional software. Whenever possible, at least three observations above the quantification limit will be used to estimate the terminal slope. The ANOVA statistics will be calculated for Cmax, AUC_{0-last}, and AUC_{0-inf}. Descriptive statistics will be calculated and reported for all PK parameters.

The NCA PK parameters will be calculated and NCA PK results sent to the FDA colleagues **before unblinding**. Summary statistics will be calculated after subsequent unblinding.

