4.2. Statistical analysis to address objective I

For bioequivalence statistics, the formulation with the larger MMAD will be treated as the reference formulation in each pairwise comparison (**Table 2**).

Table 2: Pairwise comparisons while treating the replicates of formulation 15-mm-015 separately

Comparison	Test formulation	Reference formulation
1	15-mm-016	15-mm-017
2	15-mm-015 (3a)	15-mm-017
3	15-mm-015 (3b)	15-mm-017
4	15-mm-015 (3a)	15-mm-016
5	15-mm-015 (3b)	15-mm-016
6	15-mm-015 (3a)	15-mm-015 (3b)

Bioequivalence statistics: Following the FDA guidelines ², ANOVA statistics will be performed based on ln-transformed data. For each comparison, the ratio of geometric means and the 90% confidence interval for this ratio will be calculated. We will include effects for treatment, period, sequence and subject within sequence in the ANOVA. Equivalence statistics will be performed using the equations implemented in Phoenix / WinNonlin Professional or SAS.

Reference

2. Food and Drug Administration; Center for Drug Evaluation and Research (CDER). Guidance for Industry Statistical Approaches to Establishing Bioequivalence. *FDA Guideline* 2001: 1-48.

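### Does the SAP drop the un-normalised 0.80–1.25 comparison by listing only normalised analyses?

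*SAP*

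**What the plan says.** Protocol 7.2, and the Statistical Methods part of the synopsis in the same terms, state: "ANOVA model will be used to construct univariate 90% confidence intervals for" AUC(0-t) and Cmax ratios, to be set against limits of 0.8–1.25. Neither place mentions normalisation.

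SAP section 3 adds a normalisation step: "We will use three approaches of normalizing the PK parameters". The ranking is explicit. "The normalization factors from this ex-throat approach will be used for the" primary analysis, and "Normalization factors using the FPD approach will be used as secondary analyses". For the FPD approaches, "The 15-mm-017 formulation will be used as reference (i.e. normalization factor is defined as 1.0".

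SAP 4.1 says "The ANOVA statistics will be calculated for Cmax" and the two AUCs (to the last quantifiable point and to infinity). It also has the NCA parameters calculated by subject and period and sent to the FDA before unblinding. SAP 4.2 says "ANOVA statistics will be performed based on ln-transformed data" and "For each comparison, the ratio of geometric means and the 90% confidence interval for this ratio will be calculated", for the six pairs in Table 2. Neither section says whether the values are raw or normalised, and the SAP does not restate the 0.8–1.25 limits.

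**The concern.** The two scales answer different questions. A raw ratio shows whether PK separates the formulations as dosed. A normalised ratio shows whether a difference remains once the dose reaching the lung has been corrected for. The protocol objective is whether PK is sensitive to differences in aerodynamic particle size distribution, and the raw ratio is one natural reading of it.

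If section 3 of the SAP is taken as the complete list of analyses, only dose-corrected ratios would be reported. A reader could then take a normalised verdict as the answer to the as-dosed question. The formulations differ enough in fine particle dose for the two verdicts to disagree.

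**Working it through.** **Inputs.** Fine particle doses come from SAP Table 1. The 22 completers, and CVs of 21% (at ratio 0.95) and 24% (at ratio 1.00), come from the table in protocol 7.1. Limits of 0.80–1.25 and 90% intervals come from protocol 7.2. The ANOVA terms come from SAP 4.2. I assume that normalising means dividing the PK parameter by the formulation's factor.

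**The plan's own figure.** Take two one-sided tests at 5%, σ = √ln(1+CV²), SE = σ√(2/n) and n − 2 degrees of freedom. Power is then 81.6% for case 1 (n = 40) and 83.7%, 83.1% and 81.3% for cases 2–4 (n = 22). The smallest even sample sizes reaching 80% are 40, 22, 22 and 22, as stated in the protocol.

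**Effect of normalising on the model.** ln(Y/f) = ln Y − ln f, and f is one constant per formulation. The treatment term absorbs it completely. Residuals, SE and interval width do not change. Normalised ratio = raw ratio ÷ (f_test/f_reference), so either result gives the other once the factor is known.

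**Size of the shift, secondary analyses.**

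| Pair (Table 2 comparisons) | FPD <5 µm | FPD <3 µm |
|---|---|---|
| 016/017 (1) | 18.707/12.230 = 1.530 | 9.977/5.274 = 1.892 |
| 015/017 (2, 3) | 15.869/12.230 = 1.298 | 8.599/5.274 = 1.630 |
| 015/016 (4, 5) | 15.869/18.707 = 0.848 | 8.599/9.977 = 0.862 |
| 3a/3b (6) | 1 | 1 |

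**Pass windows at the expected interval width.** Degrees of freedom are 88 − 1 − 3 − 3 − 21 = 60, and t(0.95, 60) = 1.671. At CV 24%, σ = 0.2366 and SE = 0.2366 × √(2/22) = 0.0714. The half-width factor is exp(1.671 × 0.0714) = 1.127. At CV 21% it is 1.110.

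- Raw window at CV 24%: 0.80 × 1.127 to 1.25/1.127 = 0.901–1.110. At CV 21%: 0.888–1.126.
- The normalised window, expressed as a raw ratio, is the factor times the raw window. At CV 24%, FPD <5 µm needs 1.379–1.697 for 016/017 and 1.169–1.440 for 015/017. FPD <3 µm needs 1.705–2.099 and 1.469–1.809.
- None of these overlaps the raw window at CV 24%, nor do the corresponding windows at CV 21%. For 015/016, both scales pass at CV 24% for raw ratios of 0.901–0.941 (<5 µm) and 0.901–0.956 (<3 µm).

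**Chance of showing equivalence at a true raw ratio of 1.00**, integrating over the residual variance, CV 24% (CV 21%):

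- raw scale: 85% (94%)
- FPD-normalised, comparisons 1–3: at most 1.5% (1.3%)
- FPD-normalised, comparisons 4–5: 20–27% (24–32%)

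**Is the raw analysis lost?** Three points in the text say it is not.

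1. Protocol 7.2 still names the analysis, its metrics and its limits. Nothing in the SAP withdraws it.
2. Raw parameters must exist before any normalised ones. SAP 4.1 has them calculated and sent to the FDA before unblinding, and factors specific to a formulation cannot ordinarily be applied until the treatment code is known.
3. SAP 4.1 names the ANOVA variables with no normalised qualifier. That wording accommodates a raw run as well as the runs ranked in section 3.

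**The case for a change.** The strongest case for a change is that the verdicts can be opposite. For FPD <3 µm in comparisons 1–3 no sample size lets both scales pass, because 1.630 and 1.892 exceed 1.25/0.80 = 1.5625. The SAP presents itself as the non-compartmental analysis plan, so a reader may expect it to rank every analysis. Descriptive statistics, which SAP 4.1 promises for all parameters, are no substitute for intervals against limits. Back-calculating the raw ratio for the primary analysis needs ex-throat factors that the documents do not give. A few lines of text would cost almost nothing.

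The gap in wording is real and the arithmetic is right, but the inference from them is not. That only dose-corrected ratios would be reported does not follow when SAP 4.1–4.2 leave the scale open and protocol 7.2 stands. Opposite verdicts are also no sign of a fault, since the two scales ask different questions.

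Nor would a fixed rule for reading a disagreement help, such as attributing every split to lung dose. With a true raw ratio of 1.00, the in vitro divisor alone produces the split in comparisons 1–3. That could reflect an opposing central/peripheral effect or a factor that does not track lung dose. In comparisons 4–5 it could be imprecision near a limit. Finally, protocol 7.2 states its hypothesis for formulations that differ in c/p ratio, and removing lung dose arguably serves that hypothesis better than the raw ratio does.

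**Conclusion.** No change to the plan follows. SAP 4.1–4.2 omit a cross-reference, and the omission is minor. Section 3 settles which normalised values are primary and which are secondary, and protocol 7.2 supplies the raw comparison and its limits. An analyst would run the same ANOVA on each set of values and label the tables by scale. The choice of primary is defensible and made in advance. Interval width is the same on every scale, and moving between scales takes one multiplication.

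The figures rest on several assumptions. They use FPD factors and so bear only on the secondary analyses; the shift in the primary ex-throat analysis cannot be computed. They assume division by the factor and apply 0.80–1.25 to normalised ratios, although the SAP states no limits. That protocol 7.2 means un-normalised values is inferred from its silence.

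The figures also leave out the Bonferroni-type adjustment for three comparisons in protocol 7.2. If it were applied to the intervals (one-sided 0.05/3), the 85% and 94% become about 65% and 83%. The non-overlap of windows holds at the expected interval width. For 015/017 with FPD <5 µm, an observed CV below about 18.6% would let both scales pass. The chance of observing one that low is roughly 12% if the true CV is 21%, and under 1% if it is 24%.
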